10.5 OBLIGATION OF THE INVESTIGATOR REGARDING SAFETY REPORTING

10.5.1 Definitions of adverse events

10.5.1.1 Adverse event

An **adverse event** (AE) is any untoward medical occurrence in a patient or clinical investigation patient administered a pharmaceutical product and which does not necessarily have to have a causal relationship with this treatment.

10.5.1.2 Serious adverse event

A **serious adverse event** (SAE) is any untoward medical occurrence that at any dose:

- Results in death, or
- Is life-threatening, or

Note: The term "life-threatening" in the definition of "serious" refers to an event in which the patient was at risk of death at the time of the event; it does not refer to an event which hypothetically might have caused death if it were more severe.

- Requires inpatient hospitalization or prolongation of existing hospitalization, or
- Results in persistent or significant disability/incapacity, or
- Is a congenital anomaly/birth defect,
- Is a medically important event,
 Medical and scientific judgment should be exercised in deciding whether expedited
 reporting is appropriate in other situations, such as important medical events that may not
 be immediately life-threatening or result in death or hospitalization but may jeopardize the
 patient or may require medical or surgical intervention (ie, specific measures or corrective
 treatment) to prevent one of the other outcomes listed in the definition above.

Note: The following list of medically important events is intended to serve as a guideline for determining which condition has to be considered as a medically important event. The list is not intended to be exhaustive:

- Intensive treatment in an emergency room or at home for:
 - Allergic bronchospasm,
 - Blood dyscrasias (ie, agranulocytosis, aplastic anemia, bone marrow aplasia, myelodysplasia, pancytopenia, etc),
 - Convulsions (seizures, epilepsy, epileptic fit, absence, etc).
- Development of drug dependence or drug abuse,
- ALT >3 x ULN + total bilirubin >2 x ULN or asymptomatic ALT increase >10 x ULN,
- Suicide attempt or any event suggestive of suicidality,

- Syncope, loss of consciousness (except if documented as a consequence of blood sampling),
- Bullous cutaneous eruptions.

10.5.1.3 Adverse event of special interest

An adverse event of special interest (AESI) is an AE (serious or non-serious) of scientific and medical concern specific to the Sponsor's product or program, for which ongoing monitoring and immediate notification by the Investigator to the Sponsor is required. Such events may require further investigation in order to characterize and understand them. Adverse events of special interest may be added or removed during a study by protocol amendment.

List of AESI:

- Pregnancy of a female subject entered in a study as well as pregnancy occurring in a female partner of a male subject entered in a study with IMP/NIMP,
 - Pregnancy occurring in a female patient entered in the clinical trial or in a female partner of a male patient entered in the clinical trial. It will be qualified as an SAE only if it fulfills one of the seriousness criteria (see Section 10.5.1.2),
 - In the event of pregnancy in a female participant, IMP should be discontinued,
 - Follow-up of the pregnancy in a female participant or in a female partner of a male participant is mandatory until the outcome has been determined,
- Symptomatic overdose (serious or nonserious) with IMP/NIMP,
 - An overdose (accidental or intentional) with the IMP/NIMP is an event suspected by the Investigator or spontaneously notified by the patient (not based on systematic IMP count) and resulting in clinical symptoms and/or signs and considered a "significant overdose" by the Investigator,
 - Of note, asymptomatic overdose has to be reported as a standard AE,

10.5.2 General guidelines for reporting adverse events

- All AEs, regardless of seriousness or relationship to IMP/NIMP, spanning from the signature of the informed consent form until the end of the study as defined by the protocol for that patient, are to be recorded on the corresponding page(s) or screen(s) of the CRF.
- Whenever possible, diagnosis or single syndrome should be reported instead of symptoms. The Investigator should specify the date of onset, intensity, action taken with respect to IMP, corrective treatment/therapy given, additional investigations performed, outcome, and his/her opinion as to whether there is a reasonable possibility that the AE was caused by the IMP or by the study procedure(s).
- The Investigator should take appropriate measures to follow all AEs until clinical recovery is complete and laboratory results have returned to normal, or until progression has been stabilized, or until death, in order to ensure the safety of the patients. This may imply that

observations will continue beyond the last planned visit per protocol, and that additional investigations may be requested by the monitoring team up to as noticed by the Sponsor.

- When treatment is prematurely discontinued, the patient's observations will continue until the end of the study as defined by the protocol for that patient.
- Laboratory, vital signs or ECG abnormalities are to be recorded as AEs only if:
 - Symptomatic and/or
 - Requiring either corrective treatment or consultation, and/or
 - Leading to IMP discontinuation or modification of dosing, and/or
 - Fulfilling a seriousness criterion, and/or
 - Defined as an AESI

10.5.3 Instructions for reporting serious adverse events

In the case of occurrence of an SAE, the Investigator or any designees must immediately:

- ENTER (within 24 hours) the information related to the SAE in the appropriate screens of the e-CRF; the system will automatically send a notification to the monitoring team after approval of the Investigator within the e-CRF or after a standard delay.
- SEND (preferably by fax or e-mail) a photocopy of all examinations carried out and the dates on which these examinations were performed, to the representative of the monitoring team whose name, fax number, and email address appear on the clinical trial protocol. Care should be taken to ensure that the patient's identity is protected and the patient's identifiers in the clinical trial are properly mentioned on any copy of a source document provided to the Sponsor. For laboratory results, include the laboratory normal ranges.
- All further data updates should be recorded in the e-CRF as appropriate, and further documentation as well as additional information (for laboratory data, concomitant medications, patient status, etc) should be sent (by fax or e-mail) to the monitoring team within 24 hours of knowledge of the SAE. In addition, every effort should be made to further document any SAE that is fatal or life threatening within a week (7 days) of the initial notification.
- A back-up plan (using a paper CRF process) is available and should be used when the e-CRF system does not work.

Any SAE brought to the attention of the Investigator at any time after the end of the study for the patient and considered by him/her to be caused by the IMP with a reasonable possibility, should be reported to the monitoring team.

10.5.4 Guidelines for reporting adverse events of special interest

10.5.4.1 Reporting of adverse events of special interest with immediate notification

ENTER (within 24 hours) the information related to the AESI in the appropriate AESI form of the e-CRF.

For AESIs with immediate notification, the AESI support documentation will be faxed to Quintiles Lifecycle Safety within 1 working day, even if not fulfilling a seriousness criterion, using the e-CRF.

Pregnancy:

- Pregnancy will be recorded as an AESI with immediate notification in all cases. It will be qualified as an SAE only if it fulfills the SAE criteria,
- In the event of pregnancy, IMP should be discontinued,
- Follow-up of the pregnancy is mandatory until the outcome has been determined,
- Symptomatic overdose with IMP/NIMP :
 - An symptomatic overdose (accidental or intentional) with the IMP/NIMP is an event suspected by the Investigator or spontaneously notified by the patient and resulting in clinical symptoms and/or signs and considered a "significant overdose" by the Investigator. It will be recorded in the e-CRF as an AESI with immediate notification "Symptomatic OVERDOSE (accidental or intentional)" in all cases and will be qualified as an SAE only if it fulfills the SAE criteria.

10.5.4.2 Reporting of adverse events of special interest without immediate notification

Asymptomatic overdose (accidental or intentional) with the IMP/NIMP is defined as any "significant" overdose, without clinical symptoms and/or signs, either suspected by the Investigator or spontaneously notified by the patient (not based on accountability assessment). It will be recorded as an AE "Asymptomatic Overdose (accidental or intentional)".

10.6 OBLIGATIONS OF THE SPONSOR

During the course of the study, the Sponsor will report in an expedited manner:

- all SAEs that are both unexpected and at least reasonably related to the IMP (SUSAR), to the health authorities, IECs/IRBs as appropriate and to the Investigators,
- all SAEs that are expected and at least reasonably related to the IMPs to the health authorities, according to local regulations.

In this study, some AEs are considered related to the underlying condition and thus will not be considered unexpected [please refer to the "Adverse Reaction section" in the United States Package Insert (USPI) for Lantus ((1) and Toujeo (2)].

Any other AE not listed in the "Adverse Reaction" in the USPI will be considered as unexpected.

The Sponsor will report all safety observations made during the conduct of the trial in the clinical study report.

10.7 SAFETY INSTRUCTIONS

Safety instructions are provided for SMPG (see Section 10.2.3), CGM (see Section 10.2.4), Hypoglycemia (see Section 8.2.5 and Section 9.3.1), AE, SAE (see Section 10.5.1.2), Vital Signs (see Section 10.2.1), and Obligation of the investigator regarding safety reporting (see Section 10.5).

The Investigator is the primary person responsible for taking all clinically relevant decisions on safety issues.

If judged necessary, the opinion of a Specialist should be envisaged in a timely manner (eg, acute renal failure, convulsions, skin rashes, angioedema, cardiac arrest, electrocardiographic modifications, etc.).

10.8 ADVERSE EVENTS MONITORING

All events will be managed and reported in compliance with all applicable regulations, and included in the final clinical study report.

11 STATISTICAL CONSIDERATIONS

The material in Section 11 of the clinical trial protocol constitutes the statistical analysis plan for the study. In case this plan needs revision during the study to accommodate clinical trial protocol amendments or to adapt to unexpected issues in study execution and data that affect planned analyses, a statistical analysis plan will be developed before first patient is enrolled and issued prior to database lock.

11.1 DETERMINATION OF SAMPLE SIZE

A sample size of 262 evaluable patients per treatment arm would provide at least 90% power to demonstrate superiority of Toujeo over Lantus for the primary efficacy variable of the percentage of time plasma glucose within the range of 70-180 mg/dL during Weeks 15-16 of the study. The calculations were based on a superiority hypothesis using a t-test at a 2-sided 5% significance level and assumes an absolute difference of at least 4% of time in range, a common standard deviation of 14% (assumed based on the prior AM data from the PDY12777 study), and an expected value of 53% in the Lantus arm. As a generalized linear model will be used for the primary analysis, the power should be somewhat higher due to reduced estimate variability versus the t-test.

Considering prior data from the AM arms of the PDY12777 and EDITION-4 studies, this sample size would also provide at least 80% power to demonstrate a difference in the key secondary endpoint of the rate of documented symptomatic nocturnal hypoglycemia occurring at any point post randomization, assuming a rate ratio (Toujeo over Lantus) of at most 0.86 events per pt-year. Testing of this key secondary endpoint will be considered informative if superiority of the primary endpoint is met.

Calculations were made using nQuery Advisor v6.01.

11.2 DISPOSITION OF PATIENTS

Screened patients are defined as any patient who met the inclusion criteria and signed the informed consent.

Randomized patients consist of all patients who have been allocated a treatment kit number as recorded in the IVRS/IWRS database, regardless of whether the treatment kit was used or not. Patients treated without being randomized will not be considered as randomized and will not be included in any efficacy population.

For any patient randomized more than once, only the data associated with the first randomization will be used in any analysis population. The safety experience associated with any later randomization will be assessed separately.

The safety experience of patients treated and not randomized will be reported separately, and these patients will not be in the safety population.

11.3 ANALYSIS POPULATIONS

The randomized population will include any patient who has bene allocated to a randomized treatment regardless of whether the treatment kit was used or not.

11.3.1 Efficacy populations

11.3.1.1 Modified intent-to-treat population

The efficacy analysis population will be the modified Intent-to-Treat (mITT) population, which will consist of all patients who are randomized and who have at least one post-baseline assessment of the endpoint of interest.

11.3.2 Safety population

The safety population will be comprised of all patients who take at least one dose of randomized treatment, and will be analyzed as-treated (according to the treatment actually received). In addition:

- Nonrandomized but treated patients will not be part of the safety population, but their safety data will be presented separately.
- Randomized patients for whom it is unclear whether they took the study medication will be included in the safety population as randomized.
- For patients receiving more than one study treatment during the trial, the treatment group allocation for as-treated analysis will be the treatment group in which he/she is treated for longer.

11.4 STATISTICAL METHODS

11.4.1 Extent of study treatment exposure and compliance

The extent of study treatment exposure and compliance will be assessed and summarized by actual treatment received within the safety population.

11.4.1.1 Extent of investigational medicinal product exposure

The duration of exposure during the study will be the total number of days of administration of IMP, ignoring temporary drug discontinuation. It will be calculated as (Date of the last IMP administration – date of the first IMP administration) + 1. The exposure to IMP will be summarized categorically (counts and percentages) on the safety population. If appropriate, exposure will also be summarized by starting dose.

Also dose changes from baseline at the end of treatment for IMP (U and U/kg) will be summarized by starting dose groups for the safety population.

11.4.1.2 Compliance

A given administration will be considered noncompliant if the patient did not take the planned dose of treatment as required by the protocol. Overall treatment compliance is defined as the actual number of days with at least one administration of IMP compared to the planned number of days with IMP administration during the open-label treatment periods up to treatment discontinuation.

Treatment compliance, above-planned and under-planned dosing percentages will be summarized descriptively (N, Mean, SD, Median, Min, and Max). The percentage of patients with compliance of <80% will be summarized. In addition, the number and percentage of patients with at least 1 above-planned dosing administration will be given, as well as the number and percentage of patients with 0, (0, 20%], and >20% under-planned dosing administrations. No imputation will be made for patients with missing or incomplete data.

11.4.2 Analyses of efficacy endpoints

11.4.2.1 Analysis of primary efficacy endpoint(s)

The percentage of time plasma glucose within target range of 70-180 mg/dL (3.9–10 mmol/L) during Weeks 15-16 (obtained from CGM) will be calculated based on the total time within glycemic range in the evaluable assessment interval, divided by the total time of the evaluable assessment interval.

The evaluable assessment interval for the calculation will comprise of 24-hour periods during Weeks 15-16 for which there is sufficient non-missing data. In order to be evaluable for analysis, a patient needs at least 4 days of 24-hour data meeting this criterion and should not receive protocol prohibited medication.

The endpoint will be summarized by treatment group using mean, median, standard deviation, minimum and maximum.

Differences between treatment groups will be explored using a generalized linear model, adjusting for key baseline characteristics (duration of diabetes, BMI, age and baseline value) and randomization strata. Adjusted mean estimates for each treatment with standard errors, the adjusted estimate of treatment mean difference with standard error and a 95 % confidence interval for the treatment mean difference will be provided. The statistical test will be for superiority of Toujeo over Lantus, two-sided and at a 5% significance level.

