6 STUDY DESIGN

6.1 **DESCRIPTION OF THE PROTOCOL**

LPS14587 is a multicenter, randomized, active-controlled, parallel group, 16-week open-label study. The study is a postmarketing Phase 4 trial which will recruit outpatients with type 1 diabetes mellitus who have been on basal plus mealtime insulin regimen for at least one year and currently taking a long-acting insulin analog (ie, Lantus, Toujeo, Levemir or Tresiba) plus rapidacting insulin analogs to manage their diabetes.

This is a comparative study of Toujeo versus Lantus and the comparator is Lantus. The study has an open-label design, as the injection volume of the concentrated formulation of Toujeo (glargine-U300 is distinguishable from that of the Lantus (glargine-U100) formulation of insulin glargine.

The study will be conducted in the United States with approximately 100 participating sites. It's planned to recruit 616 patients in two parallel treatment groups:

- Toujeo group, n=308 patients
- Lantus group, n=308 patients

The study consists of an up to 4-week screening and CGM training period and a 16-week treatment period. Blinded CGM (blinded to both patients and investigators) will be conducted during the weeks of the end of screening (Week -2 to 0) and end of treatment (Week 15 to 16). The CGM data will be collected for efficacy analyses.

During the screening and baseline training period, patients will wear a blinded CGM device for 7 consecutive days to generate a minimum of 4 days of usable CGM data to be eligible for randomization. Patients satisfying the inclusion/exclusion criteria and CGM requirements will be randomized 1:1 to morning injection of either Toujeo or Lantus. The randomization will be stratified by baseline HbA1c ($<8, \ge 8$), frequency of basal insulin injections BID vs QD at Visit 1, current CGM use (yes/no) at Visit 1 and mealtime insulin titration algorithm.

The protocol-mandated background therapy is mealtime insulin analogs, ie, rapid insulin analogs (eg, insulin glulisine, insulin lispro or insulin aspart), which has been used for at least 30 days before screening visit and which will be continued throughout the study. Any other glycemic lowering medications or other types of basal/bolus insulin are prohibited in this study.

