8.5 METHOD OF ASSIGNING PATIENTS TO TREATMENT GROUP

The Trial Supply Chain Manager compiles the batch number list and the Study Biostatistician provides the randomization scheme (including stratification, Section 11) to the centralized treatment allocation system (IVRS - Interactive Voice Response System /IWRS - Interactive web response system). Then, the IVRS/IWRS generates the patient randomization list according to which it allocates treatment arms to the patients.

- The treatment kits, open-label boxes identified with batch numbers, are allocated to the patients by the IVRS/IWRS using the treatment number of the boxes.
- At the screening visit the investigator or designee has to call the IVRS/IWRS to receive the patient number. The patient identification (patient number) is composed of 9-digit number containing the 3-digit country code, the 3-digit center code and the 3-digit patient chronological number (which is 001 for the first patient screened in a center, 002 for the second patient screened in the same center, etc).
- Randomization will be stratified by HbA1c obtained at the screening visit (<8.0%; ≥8.0%), Lantus (and other basal insulin analogs) injection at screening BID vs QD, current CGM use (yes/no) and mealtime insulin titration algorithm followed. For each region the IVRS/IWRS will be configured as to reach a minimum of 20% randomized patients per HbA1c strata.
- On V3 (D1), for first treatment kit(s) allocation, the investigator or designee has to call the IVRS/IWRS to provide some information (such as patient number provided by IVRS/IWRS at screening visit, date of birth, etc). Afterwards the IVRS/IWRS is called again each time a new treatment kit(s) allocation is necessary, ie, the visits as indicated in the study flowchart (Section 1.2).

- A randomized patient is a patient who has been allocated to a randomized treatment regardless whether the treatment kit was used or not (ie, patient registered by the IVRS/IWRS).
- A patient cannot be randomized more than once in the study.

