2.4.4 Analyses of efficacy endpoints

2.4.4.1 Analysis of primary efficacy endpoint(s)

The percentage of time glucose in target range 70-180mg/dL (3.9–10mmol/l) during week 16 (obtained from CGM) will be calculated based from the denominator of total time with valid data. The criteria to evaluate baseline and Week 16 CGM data are in Section 2.1.3.

The evaluable assessment interval for the calculation will comprise of 24-hour periods during Week 16 for which there is sufficient non-missing data. In order to be evaluable for analysis, a patient needs at least 4 days of 24-hour data meeting this criterion and should not receive protocol prohibited medication.

The endpoint will be summarized by treatment group using mean, median, standard deviation, minimum and maximum.

Differences between treatment groups will be assessed using a generalized linear model with identity link, adjusting for key baseline characteristics (duration of diabetes, baseline BMI, age and baseline value) and randomization strata if model permits. If model does not converge, for example due to over 90% patients fall into the carbohydrate counting, the specific factors which cause non convergence may be dropped from the model. Adjusted mean estimates for each treatment group with standard errors, the adjusted estimate of treatment mean difference with standard error and a 95 % confidence interval for the treatment mean difference will be provided. The statistical test will be for superiority of Toujeo over Lantus, two-sided and at a 5% significance level.

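### Visit 1 HbA1c enters the models only as a two-level stratum: the continuous value would add little to the primary test, but the first three main secondary models have no other glycemic covariate

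*Protocol*

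**What the plan says.** **Primary model.** Protocol 11.4.2.1 analyzes time in range of 70-180 mg/dL with a generalized linear model, "adjusting for key baseline characteristics (duration of diabetes, BMI, age and baseline value) and randomization strata". SAP 2.4.4.1 adds an identity link and a proviso: "adjusting for key baseline characteristics (duration of diabetes, baseline BMI, age and baseline value) and randomization strata if model permits". The baseline value is naturally read as baseline CGM time in range, since four usable CGM days are needed for randomization (Protocol 7.2.4, E 32).

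**Source of HbA1c.** Exclusion E 14 (Protocol 7.2.2) rests on the central-laboratory result at Visit 1, so every properly randomized patient has a value, above 6.5% and below 10%. In the primary model that value appears only through the stratum of Protocol 8.5: "Randomization will be stratified by HbA1c obtained at the screening visit (<8.0%; ≥8.0" (percent).

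**Main secondary models.** Two groups must be kept apart (Protocol 11.4.2.2, SAP 2.4.4.2).
- The last-4-hour percentage of time in 70-140 mg/dL and the coefficients of variation are analyzed as for the primary endpoint, so they carry their own baseline value.
- Nocturnal symptomatic hypoglycemia incidence (logistic) and rate (over-dispersed Poisson), and the SAP's last-4-hour mean-change mixed model, list strata, diabetes duration, BMI and age. They list neither a baseline value nor continuous HbA1c.

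SAP 2.4.4.3 tests incidence, rate and mean change as the first three secondary steps. Each later conclusion requires significance at the step before.

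**The concern.** Cutting a continuous prognostic measure into two levels discards part of its information. The sponsor evidently regards HbA1c as prognostic: the protocol synopsis says the stratification factors were chosen for their possible effect on the primary endpoint. The measured value already exists, so using it in the models would cost nothing in conduct.

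Baseline time in range may not replace it fully. It can rest on four days, recorded while some patients may only just have moved from twice-daily or evening dosing to a single morning injection (Protocol 8.2.3.1 and 10.1.1.2). HbA1c is drawn earlier and reflects a longer period.

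What is at stake is efficiency. In the hypoglycemia and mean-change models the two-level stratum is the only glycemic covariate, and these models gate the rest of the hierarchy. The hypoglycemia rate was planned with at least 80% power, against at least 90% for the primary endpoint.

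**Working it through.** **1. The plan's own figure.** Inputs from Protocol 11.1: a two-sided t-test at the 5% level; a target difference of 4 percentage points; an SD of 14 percentage points in both arms, taken from the earlier CGM study; 262 evaluable patients per arm; 1:1 allocation.

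n per arm = 2 × (1.960 + 1.282)² × 14² / 4² = 257.4, so 258. The exact noncentral t calculation gives 259. Power at 262 per arm is 0.905 (normal) or 0.904 (t). The stated size is reproduced, and it uses an unadjusted SD, so it relies on no covariate.

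**2. Information lost by the split (assumed distribution).** With HbA1c normal, mean 8, SD 0.9, truncated to 6.5-10%, the split at 8% correlates 0.82 with the continuous value. Since 0.82² = 0.67, about one third of the variance is discarded. Varying the mean (7.7 to 8.0) and SD (0.9 to 1.2) gives 0.82 to 0.83.

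**3. Gain in the primary model.** The documents give no correlations. The assumed ranges are:
- baseline with final time in range (rb): 0.5 to 0.7;
- HbA1c with final time in range (rh): -0.4 to -0.5;
- HbA1c with baseline time in range (rbh): -0.45 to -0.6.

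For two predictors, R² = (rb² + rh² - 2·rb·rh·rbh) / (1 - rbh²). For the split, multiply rh and rbh by 0.82.

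*Smallest gain* (rb 0.7, rh -0.4, rbh -0.6):
- continuous: (0.49 + 0.16 - 0.336) / 0.64 = 0.4906;
- split: (0.49 + 0.1076 - 0.2259) / 0.7579 = 0.4904;
- residual variance falls by 1 - 0.5094/0.5096, about 0.05% once unrounded values are used. That is 0.0005 × 524, or about 0.3 patients.

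*Largest gain* (rb 0.5, rh -0.5, rbh -0.45):
- continuous: (0.25 + 0.25 - 0.225) / 0.7975 = 0.3448;
- split: (0.25 + 0.1681 - 0.1513) / 0.8638 = 0.3089;
- residual variance falls by 1 - 0.6552/0.6911 = 5.2%. That is 0.052 × 524, or about 27 patients;
- the standard error falls by 1 - √0.948 = 2.6%;
- the residual SD goes from 14√0.6911 = 11.64 to 14√0.6552 = 11.33, and power at 262 per arm from 0.976 to 0.981.

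The gain vanishes when rh = rb × rbh, that is, when HbA1c predicts the endpoint only through baseline time in range. In the first case 0.7 × (-0.6) = -0.42, close to the assumed -0.40.

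**4. Cross-check by simulation.** A trivariate normal simulation kept the stratum and added continuous HbA1c beside it, with correlations before truncation of HbA1c-baseline -0.5 to -0.7, baseline-final 0.5 to 0.7 and HbA1c-final -0.3 to -0.6. The standard error fell by 0.0 to 1.8%. The largest power change was from 0.967 to 0.972.

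**5. If 14 were already the residual SD.** Power would then start at 0.905. An extra partial R² of 1%, 2% or 5% would raise it to 0.908, 0.910 or 0.919. This is not how Protocol 11.1 describes the SD, but it shows that the gain stays small.

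**6. Models without a baseline value.** In the same simulations, a linear model of final time in range without its own baseline gained 0.8 to 6.2% in standard error. This shows only that HbA1c has more room to help when no baseline value is present. It does not estimate the gain for mean change, whose correlation with HbA1c is unknown. For hypoglycemia the documents give no event rate, dispersion or association with HbA1c, so no figure can be calculated.

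**The case against.** The strongest reply is that this is discretionary. The plan prespecifies its covariates, includes the stratification factors and adjusts for the endpoint's own baseline, usually the strongest predictor. For the primary test that reply largely stands: the possible gain starts at about zero, and even its existence depends on correlations the documents do not give.

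Four stronger readings might be inferred, and the documents support none of them.
- **That the primary model treats patients at 6.6% and 7.9% as equal.** They share a stratum but can differ on continuous baseline time in range.
- **That all main secondary tests suffer alike.** The last-4-hour 70-140 mg/dL and coefficient-of-variation analyses reuse the primary model with their own baseline value.
- **That every confidence interval would narrow.** In logistic regression a prognostic covariate can raise power, but it does not shrink the standard error of the log odds ratio, and the conditional odds ratio itself changes.
- **That the HbA1c repeated-measures model exposes an inconsistency.** In the HbA1c analysis, baseline HbA1c is the outcome's own baseline. The primary model does the equivalent with baseline time in range.

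The reply does not reach the incidence, rate and mean-change models. They have no baseline value, so the argument that HbA1c is already represented does not apply there.

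**Conclusion.** The point holds as a minor, optional efficiency improvement. For the primary endpoint, and for the secondary endpoints that reuse its model, the gain is about zero to 5% of residual variance. For the primary test that means a standard error about 0 to 2.6% smaller and at most about half a point of power, with 14 read as the unadjusted SD. All of this rests on the assumed HbA1c distribution and correlations.

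A reader might infer that the planned power is at risk. It is not: "A sample size of 262 evaluable patients per treatment arm would provide at least 90% power to demonstrate superiority of Toujeo over Lantus" reproduces with no adjustment at all. Type I error and freedom from bias are also unaffected.

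The better reason to act lies in secondary steps 1 to 3, where the two-level stratum is the only glycemic covariate. The size of the benefit there is unknown, and it could be small if HbA1c is only weakly related to those outcomes. In the logistic model any benefit would come as power. In the over-dispersed Poisson model it would come through a lower dispersion estimate.

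**What to change.** Before database lock, add continuous Visit 1 central-laboratory HbA1c to the covariate lists below, and keep the randomization strata in each:
- nocturnal symptomatic hypoglycemia incidence and rate: Protocol 11.4.2.2 and SAP 2.4.4.2 (SAP 2.4.5.3 repeats the covariate list for the safety population and should match);
- last-4-hour mean change: SAP 2.4.4.2;
- primary model: Protocol 11.4.2.1 and SAP 2.4.4.1. The endpoints analyzed as for the primary endpoint then follow.

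The first two matter most. The trial is open-label, so record the change as made without reference to results by arm.

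The cost is a few words and one degree of freedom per model. No new data, visits or patients are needed.
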